1.2 Secondary Objectives

- Compare the distribution ^{18}F -DCFBC with multiparametric MRI and whole mount histopathology in patients undergoing prostatectomy
- Evaluate the distribution ^{18}F -DCFBC uptake in prostate cancer patients with biochemical relapse (site of recurrence unknown)
- Compare focal ^{18}F -DCFBC uptake with focal abnormalities identified on standard of care imaging
- Compare the uptake of ^{18}F -DCFBC in bone with respect to Na^{18}F PET/CT in patients with metastatic disease (the emerging gold standard, for detection of bony metastases).
- Evaluate the change over time in ^{18}F -DCFBC distribution in patients with known metastatic disease with clinical follow-up data 4-6 months post baseline ^{18}F -DCFBC PET/CT (e.g. understand the effect of androgen deprivation therapy (ADT) on ^{18}F -DCFBC uptake)

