To date 31 patients have been scanned on Arm 2. All are assumed to have recurrent disease based on rising PSA. There have been 20 positive scans (9 in the prostate bed, 8 outside the prostate bed (nodes or bone) and 3 both in and out of the prostate bed. Biopsy is only available in 7 but clinical information is supportive (i.e. response to therapy) in 4 more. Thus, the results are still preliminary. In the range of PSA 0.2-0.5ng/ml the scan is 25% positive, 0.5-1.0 ng/ml 50% 1.0 to 2.0ng/ml 40% and >2.0ng/ml 85%. However, the first 10 patients were done without irrigation catheters and this undoubtedly explains some of the findings. The first expansion request for Arm 2 was to get more patients with bladder irrigation catheters after we recognized that bladder-urethra activity was probably hiding some lesions. We now have over 20 patients in that category. Having shown some promising results, the purpose of this expansion cohort is to better define the sensitivity of DCFBC as a function of serum PSA. This should be a useful metric for comparing DCFBC with the next agent, DCFPyl which is reputed to have higher sensitivity. Thus, the basis of our request is to obtain more accurate assessment of the sensitivity of this agent as a function of PSA in patients with biochemical recurrence.

CC Protocol Number: 14-C-0140
Abbreviated Title: DCFBC in prostate cancer
Version date: 10/27/2015
CIP #: 9622

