4 STUDY IMPLEMENTATION

4.1 Study Design

This is an open-label, 3-armed single-center pilot study. 110 evaluable subjects will be enrolled into the study (12 evaluable patients in arm 1; 78 evaluable patients in arm 2, and 20 evaluable patients in arm 3). An evaluable patient is defined as a patient who completes all required study procedures according to the assigned study arm. In order to allow for a small number of nonevaluable patients, the accrual ceiling will be set at 125.

Informed consent will be obtained prior to study enrollment. All subjects will undergo ^{18}F DCFBC injection and PET/CT imaging.

Patients in Arms 1 and 2 will undergo a single ^{18}F DCFBC PET/CT.

Patients in Arm 1 will have undergone a standard of care biopsy or clinically indicated prostatectomy. Specimens will be whole mounted on glass slides and regions of malignant tumor will be marked by the pathologist.

When possible, uptake of ^{18}F DCFBC depicted on PET/CT in Arms 2 and 3 will be validated with biopsy.

Patients in Arm 2 will be followed for clinical, imaging or pathologic data that may be obtained by their medical team within 12 months of imaging to determine if associations with ^{18}F DCFBC PET/CT can be seen.

CC Protocol Number: 14-C-0140
Abbreviated Title: DCFBC in prostate cancer
Version date: 10/27/2015
CIP #: 9622

Subjects in the metastatic disease arm (Arm 3) (as well as individuals who cross over into Arm 3) will undergo 2 separate ^{18}F DCFBC PET/CT imaging sessions, one at initial enrollment, and a second upon clinical follow-up (4-6 months after baseline ^{18}F DCFBC).

Patients in Arm 3 will also undergo a whole body Na^{18}F PET/CT scan within 3 weeks of each ^{18}F DCFBC to assess for potential early bone metastases. Changes in distribution of each radiotracer over the 4-6 month period will be compared with clinical data and imaging (obtained as standard of care) at that time. Each ^{18}F DCFBC PET/CT will be compared with the corresponding Na^{18}F PET/CT scan when obtained.

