14 STATISTICAL CONSIDERATIONS

14.1 Primary Analysis

This is a single site three-arm pilot study, where prostate cancer patients are enrolled into different arms according to their disease types: localized (Arm 1), recurrent (Arm 2) or metastatic (Arm 3). The primary objective of this study is to assess the ability of ^{18}F -DCFBC to identify sites of localized, recurrent and metastatic prostate cancer. To achieve this goal, ^{18}F -DCFBC PET/CT and conventional imaging will be used to identify positive suspected sites, and the proportion of positive concordance will be used to assess the performance of ^{18}F -DCFBC. In a recent study (Cho et al., 2012), 32 positive suspected sites in five prostate cancer patients with metastasis were identified by ^{18}F -DCFBC PET/CT with 21 concordant on both ^{18}F -DCFBC PET/CT and conventional imaging. At the individual level, the number of positive suspected sites ranged from 2 to 12 with the patient-specific concordance rate ranging from 0 to 100%. The overall concordance rate which was the average of individual-specific estimates across patients equaled 64% with corresponding standard deviation equal to 43%. For the new study, assume that for patients in Arm 1 and Arm 3, the mean concordance rate is 70% with 43% standard deviation as observed in Cho et al. With 12 evaluable patients in Arm 1, the 90% expected confidence interval for the mean concordance rate is (0.50, 0.90). With 20 evaluable patients in Arm 3, the 90% expected confidence interval for the mean concordance rate is (0.54, 0.86). For patients in Arm 2 (recurrent disease), it is unlikely to identify suspected lesions by conventional imaging at the baseline. These patients will be followed according to the protocol.

Amendment E Addendum:

Sensitivity of ^{18}F -DCFBC uptake in prostate cancer patients in Arm 2 is evaluated by its ability in differentiating mean values of PSA between PET-CT positive and PET-CT negative patients. To this end, the current study with sample size 35 for Arm 2 is under-powered to detect a sizeable mean difference in PSA between the two groups. Based on the preliminary data of the study, log-transformed PSA is approximately normally distributed with standard deviation equal to 1.3. Assume 1:2 allocation of PET-CT negative vs. PET-CT positive

CC Protocol Number: 14-C-0140
Abbreviated Title: DCFBC in prostate cancer
Version date: 10/27/2015
CIP #: 9622

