patients. The current study has only 48% power to detect a 2.5-fold geometric mean ratio in PSA between the two groups at the 5% significance level using a two-sided Wilcoxon test. To achieve 80% power, 26 PET-CT negative and 52 PET-CT positive patients are required. These results are based on 2000 Monte-Carlo samples from the normal distributions. Under the alternative hypothesis, $\log(\text{PSA})$ is assumed to follow a normal distribution with mean (SD) equal to 0.06 (1.3) and 0.98 (1.3) for the PET-CT negative and PET-CT positive group, respectively. The mean difference of 0.92 ($=0.98-0.06$) in log scale of PSA corresponds to a 2.5-fold geometric mean ratio in the original scale.

In order to allow for the possibility of a small number of unevaluable patients, the accrual ceiling will be set at 15, 85 and 25, yielding a target ceiling of 125 patients for this study.

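### The only Arm 2 analysis with a stated method, a Wilcoxon comparison of PSA by scan result, yields no detection rate at any PSA, although Arm 2 was expanded to define sensitivity as a function of PSA.

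*Combined protocol and SAP*

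**What the plan says.** Section 2.3 (Amendment E Addendum) states that "the purpose of this expansion cohort is to better define the sensitivity of DCFBC as a function of serum PSA", and repeats this as the basis of the request. The intended use is explicit: "This should be a useful metric for comparing DCFBC with the next agent". It reports interim positivity by PSA band, beginning "In the range of PSA 0.2-0.5ng/ml the scan is 25% positive" and continuing with 50% at 0.5-1.0, 40% at 1.0-2.0 and 85% above 2.0 ng/ml, with no denominators or intervals. Positivity stands in for sensitivity because "All are assumed to have recurrent disease based on rising PSA". The same paragraph says the first 10 of the 31 men were scanned without irrigation catheters and that this accounts for some of the results.

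Section 14.1 (Amendment E Addendum) says that in Arm 2 sensitivity is "evaluated by its ability in differentiating mean values of PSA between PET-CT positive and PET-CT negative patients". The arm is sized for a comparison of PSA between those groups "using a two-sided Wilcoxon test" at the 5% level. The inputs are log-PSA means of 0.06 (negative) and 0.98 (positive), SD 1.3, and a 1:2 split of negative to positive scans. The stated power is 48% with 35 men and 80% with 26 + 52 = 78.

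Other Arm 2 items carry no method. Section 1.2 lists evaluating the distribution of "uptake in prostate cancer patients with biochemical relapse (site of recurrence unknown"). Section 4.1 collects follow-up data "within 12 months of imaging to determine if associations with" the scan result can be found. Section 14.1 says conventional imaging is unlikely to show lesions at baseline in Arm 2, so the concordance rate does not serve there. Section 14.2 names methods for localized and metastatic disease only, and section 14.3 excludes Arm 2.

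**The concern.** Sensitivity as a function of PSA is a probability of a positive scan given PSA. The planned test runs the other way: it conditions on the scan result, compares PSA, and returns a p-value. Followed to the letter, the plan would finish Arm 2 without a planned detection rate, or an interval for one, at any PSA.

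Arm 2 is 78 of the 110 evaluable patients (71%). A later comparison with the next agent would rest on estimates chosen after the data were seen, or on band percentages without denominators or intervals, like the interim ones in section 2.3. Arms 1 and 3 do have expected confidence intervals for their rates in section 14.1; Arm 2 has none.

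**Working it through.** **Inputs (section 14.1).** Log PSA is N(0.06, 1.3) in scan-negative and N(0.98, 1.3) in scan-positive men; difference 0.92; 26 negative and 52 positive (earlier target 35, taken as 12 and 23); two-sided 5% Wilcoxon test. PSA bands are from section 2.3, plus one below 0.2 ng/ml, because section 3.1.5.2 admits men after radiation with any rise from nadir.

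**Step 1: the plan's own figure.** Simulating the Wilcoxon test from these normals (4,000 to 20,000 trials per run) gives 81% power at 26/52 (stated 80%) and 46-47% at 12/23 (stated 48%). The t-test approximation is a check from above: 0.92 / (1.3 × √(1/26 + 1/52)) = 0.92 / 0.312 = 2.95, and Φ(2.95 − 1.96) = 84%, slightly higher as expected. Also exp(0.92) = 2.51, the stated 2.5-fold ratio. The sample size is sound for its own test.

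**Step 2: what the test leaves undetermined.** With equal SDs, Bayes' rule gives

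logit P(positive | PSA) = log[π/(1 − π)] + (0.92/1.3²) × (log PSA − 0.52),

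where π is overall positivity and 0.52 = (0.06 + 0.98)/2. The slope is 0.92/1.69 = 0.544. At PSA 0.35 ng/ml, log PSA = −1.050, so the second term is 0.544 × (−1.570) = −0.855.

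- π = 1/3: logit = −0.693 − 0.855 = −1.548, positivity 18%.
- π = 2/3: logit = 0.693 − 0.855 = −0.161 (before rounding of the terms), positivity 46%.

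Wilcoxon power is about 80% in both cases (52/26 and 26/52 are mirror splits). The effect being tested is the same, but the detection rate differs by 28 percentage points.

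**Step 3: what 78 men can give.** Expected men in a band = 26 × P(band | negative) + 52 × P(band | positive). For 0.2-0.5 ng/ml: 26 × 0.182 + 52 × 0.076 = 4.7 + 3.9 = 8.7, with implied rate 3.9/8.7 = 46% before rounding. The 95% Wilson width is 2z√(p(1 − p)/n + z²/4n²) / (1 + z²/n), averaged over simulated trials.

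| PSA (ng/ml) | Expected men (n = 78) | Implied positivity | Mean Wilson width, n = 78 | Mean Wilson width, n = 35 |
|---|---|---|---|---|
| < 0.2 | 4 | 32% | 0.65 | 0.73 |
| 0.2-0.5 | 9 | 46% | 0.54 | 0.66 |
| 0.5-1.0 | 12 | 56% | 0.49 | 0.62 |
| 1.0-2.0 | 15 | 65% | 0.43 | 0.57 |
| > 2.0 | 39 | 79% | 0.25 | 0.36 |

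A logistic curve on log PSA gives mean widths of 0.36, 0.28, 0.23 and 0.22 at 0.35, 0.75, 1.5 and 3.0 ng/ml. These narrower intervals assume a linear logit, which the plan's equal-SD normals guarantee but real data need not follow.

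**The case against.** The strongest reply is that the Wilcoxon test is not beside the point. Under the plan's normals, the mean difference divided by the variance is exactly the logistic slope of positivity on log PSA. Power for that slope is close to the Wilcoxon's (about 82-84% by logistic regression against 81%), and with a flat positivity profile the test rejects only about 5% of the time. It therefore does test whether detection depends on PSA. That stands, and a reader who inferred that the test says nothing about PSA dependence would go too far. What is missing is planned estimation.

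Second, section 14.1 says openly how sensitivity will be assessed, this is a pilot, and section 2.3 shows the team already tabulating positivity by band. This limits the practical harm, since the data will exist and can be tabulated. But section 14 then replaces the quantity on which section 2.3 based its request, and the existing table has neither denominators nor intervals.

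Third, even a planned estimate will be imprecise below 2 ng/ml. True; stating this in advance is part of the remedy.

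A reader might also take the interim 25/50/40/85% pattern as evidence that a smooth logistic curve would mislead. The documents do not support that: the denominators are not given, the dip at 1.0-2.0 may be noise, and 10 of the 31 men were scanned without irrigation.

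**Conclusion.** The concern holds as a mismatch between the stated purpose of the Arm 2 expansion and its planned analysis. The plan tests for an association between PSA and scan result but plans no positivity rate or interval at any PSA, for 71% of the evaluable patients. It should be fixed, but it does not put the trial in doubt.

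A reader might infer that n = 78 or the stated power is wrong. Neither is: both reproduce to within 2 percentage points.

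The gap itself follows from the text alone. The band counts, implied rates and interval widths rest on the plan's normal model with a 1:2 split. Reading positivity as sensitivity rests on the assumption in section 2.3 that every Arm 2 man has recurrence.

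**What to change.** In section 14.1:

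- Make the main Arm 2 estimate the patient-level positivity rate by PSA: observed proportions with denominators and 95% Wilson intervals in the section 2.3 bands, plus a band below 0.2 ng/ml.
- Add a logistic curve on log PSA as a secondary summary beside the bands, noting that its narrower intervals assume a linear logit.
- Keep the Wilcoxon test as supportive and keep n = 78.
- State the expected precision: about 4, 9, 12, 15 and 39 men, with mean interval widths of about 0.65, 0.54, 0.49, 0.43 and 0.25.
- Show the rates by actual catheter use as well, given what section 2.3 says about the first 10 men.
- State that positivity equals sensitivity only if every Arm 2 man has recurrence.

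The cost is SAP wording, one table with a plot and a little more analysis. There are no new patients, visits or scans: PSA is already collected, and the positive or negative call per patient is one the Wilcoxon test already needs. The downside is that the intervals below 2 ng/ml will be visibly wide.

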14.2 Secondary Analysis

For patients with localized disease, the diagnostic accuracy of ^{18}F -DCFBC PET/CT will be compared with multiparametric MRI using the sector-based analysis. Patient-specific sensitivity and specificity will be estimated and differences in sensitivity and specificity between different modalities will be tested by the Wilcoxon signed-rank test. Change of ^{18}F -DCFBC uptake for patients with metastatic disease over time will be estimated by the linear mixed effect model where random intercept will be used to account for the intra-patient correlation of longitudinal ^{18}F -DCFBC uptake. In addition, in patients with metastatic prostate cancer to bone, the uptake of ^{18}F -DCFBC will be correlated with the uptake of the emerging gold standard, ^{18}F Sodium Fluoride PET/CT by the Spearman rank correlation.

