This is a single site 3-arm study enrolling a total of 110 evaluable patients: Arm 1 will include 12 patients with presumed localized prostate cancer scheduled to undergo prostatectomy or biopsy within 4 months of enrollment; Arm 2 will include 78 patients with biochemical recurrence without evidence of metastasis on conventional imaging; and Arm 3 will include 20 patients with known metastatic disease who may or may not be on or/scheduled to begin therapeutic intervention. Patients with presumed localized disease will undergo a standard of care, clinical multiparametric endorectal coil MRI in the NCI Molecular Imaging Clinic within 4 months of screening. Patients in Arm 3 will undergo 2 imaging sessions: baseline and 4-6 month follow-up. Clinical records (including PSA) and treatment (if any) that occurred in the imaging interval must be available. All patients in Arm 3 will also undergo Na¹⁸F PET/CT for evaluation of bone metastases as part of this protocol. In order to allow for a small number of nonevaluable patients, the accrual ceiling will be set at 125.

CC Protocol Number: 14-C-0140
Abbreviated Title: DCFBC in prostate cancer
Version date: 10/27/2015
CIP #: 9622
Imaging Schema

ARM 1 Suspected localized prostate cancer

[figure not shown]

*Biopsy is standard of care at NCI, prostatectomy will only be performed if clinically indicated and patient wishes to pursue this form of treatment

ARM 2 (biochemical recurrence)

ARM 3 (known metastasis)

Each set of $Na^{18}F$ PET/CT and ^{18}F -DCFBC PET/CT will be done within 3-weeks of each other.

TABLE OF CONTENTS

Summary of Changesiv

Protocol.....iv

Précis.....4

Background4

TABLE OF CONTENTS7

1 Study Objectives10

1.1 Primary Objective.....10

1.2 Secondary Objectives.....10

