4.9.2 Pathologic and Imaging Correlation

NIH Clinical Center prostatectomy or standard of care biopsy is planned for subjects enrolled in ARM 1 (localized disease). The specimen results will be correlated with ¹⁸F DCFBC PET/CT and MRI results.

Following radical prostatectomy, surgical specimens will undergo standard preparation and sectioning in the Department of Surgical Pathology for pathological diagnosis. Urologists from the UOB at the NIH Clinical Center have extensive experience with laparoscopic prostatectomy. The surgical specimen obtained with the laparoscopic procedure is preserved at least as intact as in open laparotomy procedures. To date, the UOB has performed over 250 MRI/pathology correlations after laparoscopic prostatectomies.

At resection, the specimen is painted with three different colored inks (anterior right with blue, anterior left with red and urethral side with yellow) for correct orientation, and the gland is left to dry for 1-2 minutes. The gland is divided into two equal parts in the axial plane; from one of these parts, a rectangular sample of 2x1x0.2 cm is taken for DNA analysis – it is understood that this sample may contain cancer tissue and may not be reported. The DNA analysis is for research interest of the NCI and is not a component of this protocol. The two cut parts are re-glued for fixation. Fresh prostate gland is hard to hold and cut, so slicing after fixation is better and easier. The glued and combined gland is kept in formalin for 24 to 48 hours at room temperature for fixation. After fixation, the seminal vesicles are removed and then the gland is sliced via a custom-made mold based on the 3D imaging information from high resolution T2W MR images. The molds are equipped with slots spaced 6 mm apart. The gland only shrinks by approximately 3% after the first fixation and prior to slicing. A single-blade steel knife is used for one prostate. In this manner, attempts will be made to cut the specimens in the same plane as the imaging was performed. The sliced gland is kept within formalin for as long as a week at room temperature. The tissue is processed into paraffin blocks and sectioned by standard methods. The gland shrinks by 10-15% after all of these procedures.

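### Section 14.2 tests PET against MRI by sector in all localized patients, although objective 1.2 covers only prostatectomy patients and biopsy-only men have no reference standard in unsampled sectors

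*Combined protocol and SAP*

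**What the plan says.** Section 14.2 opens the analysis with "For patients with localized disease, the diagnostic accuracy of" PET/CT, which "will be compared with multiparametric MRI using the sector-based analysis". Sensitivity and specificity are estimated within each patient, and "differences in sensitivity and specificity between different modalities will be tested by the Wilcoxon signed-rank test". As worded, the population is the whole of Arm 1.

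The corresponding objective in Section 1.2 is narrower. It compares the PET distribution "with multiparametric MRI and whole mount histopathology in patients undergoing prostatectomy".

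Arm 1 is not a prostatectomy cohort. The précis says that "Arm 1 will include 12 patients with presumed localized prostate cancer scheduled to undergo prostatectomy or biopsy within 4 months of enrollment", and the Arm 1 schema footnote adds that "prostatectomy will only be performed if clinically indicated and patient wishes to pursue this form of treatment". Section 4.9.2 accepts either kind of specimen for correlation with PET and MRI. The patient-specific molds that align histology with imaging are described only for prostatectomy specimens (Sections 4.7.1 and 4.9.2).

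No section defines the sectors, names the reference standard for the Section 14.2 comparison, describes the biopsy scheme, or says how an unsampled sector is scored. Section 4.9.3 uses other units for comparing PET with MR: the subject and the lesion.

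**The concern.** Sector-level sensitivity and specificity need a known truth in every sector that is scored. Whole-mount histology supplies it across the gland. A biopsy supplies it only where a core was taken.

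The unsampled sectors may also not be a neutral subset. Section 3.1.5.1.1 requires a suspicious MRI with a lesion of at least 6 mm, and histologic confirmation before the PET scan. The confirming biopsy therefore cannot have been guided by PET and may well have been guided by MRI. Section 4.8 does not require biopsy of PET-positive foci. If sampling does follow MRI, cancers that MRI missed tend to go unverified, while those it found are counted.

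What is at stake is whether a reported PET-MRI difference reflects the two modalities, or reflects where the needle went and how the gaps were scored.

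**Working it through.** Section 14.2 gives no sample size, power or significance level for this comparison, so there is no planned figure to reproduce. The sampling effect can be sized under assumptions.

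**Assumed inputs (none is in the documents).** Both modalities have sensitivity s = 0.6 and specificity 0.9. There are 12 sectors, 2 or 3 with cancer. All MRI-positive sectors are sampled, together with a fraction q of MRI-negative sectors. A core detects any cancer in the sector it samples.

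**Sensitivity.** Let b be the probability that both modalities are positive in a cancer sector.
- Apparent MRI sensitivity = s / (s + (1 − s)q) = 0.6 / (0.6 + 0.4q).
- Apparent PET sensitivity = (b + (s − b)q) / (0.6 + 0.4q).
- Independent detection: b = 0.6 × 0.6 = 0.36.
- Correlation of 0.5 within cancers: b = 0.36 + 0.5 × 0.24 = 0.48.

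| q | MRI | PET, independent | PET, correlation 0.5 |
|---|---|---|---|
| 0 | 100% | 60% | 80% |
| 0.5 | 75% | 60% | 67.5% |
| 0.8 | 65% | 60% | 63% |
| 1 | 60% | 60% | 60% |

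These figures are the same whether unsampled sectors are scored negative or dropped, because an unsampled sector is never reference-positive.

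**Specificity, unsampled sectors scored negative.** Unverified cancers join the reference-negative sectors. All of them are MRI-negative, and under independence 60% are PET-positive.
- q = 0, 2 cancers: PET (9 + 0.32)/10.8 = 86%; MRI (9 + 0.8)/10.8 = 91%.
- q = 0, 3 cancers: PET (8.1 + 0.48)/10.2 = 84%; MRI (8.1 + 1.2)/10.2 = 91%.
- q = 0.5: PET (9 + 0.16)/10.4 = 88% or (8.1 + 0.24)/9.6 = 87%; MRI (9 + 0.4)/10.4 = 90% or (8.1 + 0.6)/9.6 = 91%.

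**Specificity, unsampled sectors excluded.** Apparent MRI specificity = 0.9q / (0.1 + 0.9q). This is 0% at q = 0 and 0.45/0.55 = 82% at q = 0.5. PET stays at 90% under independence. The lean has reversed.

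**Effect of the entry rule.** The formulas above ignore selection on a positive MRI. A simulation of equally accurate, independent modalities added it by keeping only patients with at least one MRI-positive cancer sector. It assumed 6, 12 or 20 sectors, sector prevalence 0.15 to 0.35, sensitivity 0.6 to 0.7, specificity 0.85 to 0.90, and systematic-core sensitivity 0.6. PET minus MRI came out as follows.

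| Verification | Sensitivity | Specificity, unsampled = negative | Specificity, unsampled excluded |
|---|---|---|---|
| MRI-positive sectors only | −0.30 to −0.40 | −0.03 to −0.10 | +0.85 to +0.90 |
| Plus systematic cores in half the sectors | −0.21 to −0.26 | −0.02 to −0.07 | +0.06 to +0.10 |
| Systematic cores in all sectors | −0.04 to −0.10 | about 0 | not applicable |
| Whole mount | −0.04 to −0.11 | about 0 | not applicable |

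**Signed-rank test in a smaller group.** With k non-zero differences, the smallest exact two-sided p-value is 2/2^k: 0.0625 at k = 5 and 0.031 at k = 6.

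**The case against.** Section 14.2 may simply abbreviate objective 1.2. The objective names prostatectomy patients, and only their specimens are molded and aligned, so an analyst might restrict the comparison without being told to. This is also an unpowered secondary analysis in a 12-patient pilot arm. No sample size depends on it, and Section 16.4 says treatment decisions will not rest on PET findings. These points limit the consequence. They do not settle the population, because Section 14.2 says localized disease without restriction and Section 4.9.2 accepts biopsy results for correlation.

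The stronger objection concerns direction. A reader might infer that including biopsy-only men biases the whole comparison toward MRI. The documents do not support that:
- The biopsy scheme is not stated. Section 13.1 refers to an NIH routine clinical protocol that is not reproduced, and the Arm 1 schema figure is not shown. With systematic sampling of every sector, biopsy did no worse than whole mount in the simulation.
- Section 4.11 places a surgery or biopsy after PET, and under Section 4.8 suspicious foci are communicated to the referring physician. A later biopsy could therefore be informed by PET.
- The 60% for PET depends on independent detection. At a correlation of 0.5 the gap falls from 40 to 20 points at q = 0, and from 15 to 7.5 points at q = 0.5.
- If unsampled sectors are excluded, specificity leans toward PET.

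All of this stands, so the direction can be stated only conditionally.

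**Conclusion.** The mismatch holds. As written, Section 14.2 admits men without whole-gland truth to a sector-level accuracy test that objective 1.2 reserves for prostatectomy patients.

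If sampling is MRI-directed, MRI sensitivity is inflated relative to PET: by 40, 15 or 5 points at q = 0, 0.5 or 0.8, assuming 60% sensitivity and independent detection. The gap is smaller if the modalities tend to find the same cancers, and the sampling effect vanishes with full systematic sampling. The sign of the specificity difference depends on a scoring choice the plan does not make.

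A reader might also infer that whole-mount verification makes the comparison unbiased. It does not: every Arm 1 patient enters with a suspicious MRI. In the simulated scenarios MRI kept a sensitivity advantage of about 0.04 to 0.11 over an equally accurate PET.

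If all 12 men had prostatectomy, the population mismatch would have no effect. The plan does not fix that number.

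**What to change.** In Section 14.2:
1. Restrict the sector-based sensitivity, specificity and signed-rank test to patients with whole-mount prostatectomy, matching objective 1.2. Name whole-mount histology as the reference standard and define the sectors.
2. Report biopsy-only patients separately and descriptively, using sampled sectors only and no test. Note that specificity is then distorted in PET's favour if sampling followed MRI.
3. State that MRI sensitivity is conditional on MRI-positive entry, including in the prostatectomy patients.

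This is a wording change and no sample size moves. The cost is that fewer than 12 patients may contribute. Assuming a two-sided 5% level, which Section 14.2 does not state, the exact signed-rank test cannot reach significance with fewer than 6 non-zero differences. In that case only estimates should be reported.
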